3 INTRODUCTION AND BACKGROUND

3.1 *Introduction*

Acute liver failure (ALF) is a rare disorder affecting an estimated 2000 patients annually in the United States (US). Hepatotoxicity related to the use of acetaminophen is the most common etiology of ALF in the US (1).

Acute liver failure is the result of massive damage to previously normal liver parenchyma with resultant loss of liver function. As the hepatocyte function is lost, the liver loses its ability to synthesize proteins and extract circulating toxins. The two cardinal signs of ALF, coagulopathy and encephalopathy, represent the loss of the ability to synthesize clotting factors and to remove ammonia, respectively.

Acute liver failure often affects young people and carries a very high mortality. Only 45% of patients with ALF will spontaneously recover. Of the remaining 55%, 30% will die and 25% will undergo an emergency liver transplantation. Emergency liver transplantation in this setting has a 90% 1-month survival rate and a 70% 1-year survival rate. Mortality in ALF can be due to a variety of factors, including sepsis and multi-organ system failure, but cerebral edema due to increased ammonia resulting in intracranial hypertension and brainstem herniation is one of the most common causes of death, accounting for 30% of the mortality in this population (2).

There is strong experimental and clinical rationale for the use of ammonia-lowering therapies in ALF. Ammonia is normally produced in the gut and transformed by the liver into urea. As the liver fails, ammonia increases in the systemic circulation and enters into the brain. The result of a rapid rise in ammonia in the cerebral circulation is hepatic encephalopathy (HE), a reversible neuropsychiatric condition that ranges in severity from mild impairment in attention, to delirium, coma and death. A particular concern regarding HE in ALF is that ammonia level increases tend to be very rapid. This rapid rise in ammonia does not provide sufficient time for brain cells to compensate, with the end result being astrocyte swelling with increased intracranial pressure (ICP) and ultimately, death due to brain herniation. An arterial ammonia level above 150 μ M has been shown to correlate with a poor prognosis, and is almost universally indicative of increased intracranial pressure (3).

Cerebral edema in patients with ALF results from overloading brain astrocytes with ammonia. Astrocytes utilize the same mechanism as skeletal muscle to detoxify ammonia (*i.e.*, amidation of glutamate to glutamine via glutamine synthetase). The resulting accumulation of brain glutamine results in impaired astrocyte osmoregulation, astrocyte swelling and cerebral edema (4-6). Astrocytes contain counter-regulatory mechanisms to offset increased intracellular osmotic pressure, but compensate too slowly in the acute situation.

Cortical astrocyte swelling is the most common neuropathological observation in post-mortem brains of ALF patients. Cerebral edema is found in up to 80% of patients who die of ALF and is nearly universal among patients with coma (7). There are clear associations between arterial ammonia levels, uncal herniation, and death in patients with ALF (3,8). There is also clear evidence of these associations in animal models of ALF(9-12).

OCR-002 (L-ornithine-phenylacetate) is an ammonia detoxification agent that works by

eliminating ammonia in the circulation, with the expectation that it will result in a more rapid reduction than current therapies, and a lower incidence of cerebral edema.

3.2 Physical, Chemical, and Biological Characteristics of OCR-002

[figure not shown]
Background information on OCR-002 is summarized below. More detailed information is provided in the Investigator's Brochure.

3.2.1 Chemistry

OCR-002 is an ammonia detoxification agent and has the chemical name L-ornithine·phenylacetate (L-ornithine·benzeneacetate salt (1:1), CAS-RN 952154-79-9). The molecular formula is $C_8H_7O_2 \cdot C_5H_{13}N_2O_2$ and OCR-002 has a molecular weight of 268.31 g/mole.

OCR-002 drug substance is a new chemical entity and exists as a single crystalline molecular structure as an ornithine salt of phenylacetate as shown below:

Figure 1: L-ornithine·phenylacetate

3.2.2 Summary of Nonclinical Safety Data

The nonclinical safety of OCR-002 was evaluated in a comprehensive program of *in vitro* and *in vivo* studies which included evaluation of the potential undesirable pharmacodynamic effects of OCR-002 on physiological functions in relation to exposure in the therapeutic range and above (safety pharmacology core battery), evaluation of the mutagenic and clastogenic potentials of OCR-002 (*in vitro* test battery for genotoxicity), and evaluation of the short- and longer-term functional and morphologic effects associated with OCR-002 exposure in whole animal models (mammalian toxicology program). The results of the OCR-002 toxicology program indicate a low potential for systemic toxicity in humans. Please refer to the OCR-002 Investigator's Brochure for a detailed discussion.

Further evidence of safety is provided by over 20 years of clinical experience with Ammonul® (sodium phenylacetate and sodium benzoate) Injection 10%/10% and Hepa-Merz™ (L-ornithine L-aspartate). The safety profiles of these entities are discussed in the Investigator's Brochure.

3.3 Rationale for the Study and Dose Selection

3.3.1 Rationale for the Study

There is no established medical therapy for ALF (13). Investigational agents such as charcoal

hemoperfusion and administration of prostaglandin E1, which showed early promise, have not been shown to be superior to standard of care when analyzed in randomized controlled studies (14-17). Plasmapheresis and hepatectomy have been suggested as possible “bridges” to liver transplantation but a prospective trial of the former has been presented in abstract form only. Hypothermia has been investigated in a total of only 38 patients with ALF, all from Jalan, *et al* (18), and may be an effective bridge to liver transplantation (19). However, therapeutic hypothermia has considerable potential adverse effects and has never been shown to increase spontaneous (non-transplant) survival. External bio-artificial livers such as the MARS device have been employed, but use of these devices remains experimental, and the preliminary results have been generally disappointing (20).

Treatment strategies focusing on the specific underlying conditions are, for the most part, of little or no use once ALF has occurred. Corticosteroids for fulminant autoimmune hepatitis, chelation therapy for fulminant Wilson’s disease, and anti-viral therapies for fulminant hepatitis B have never been shown to be of benefit in the setting of ALF, and supportive care and liver transplantation are the only treatment strategies that can be used in these patients (21-23).

One notable exception to this is the use of *N*-acetylcysteine (NAC) for ALF due to acetaminophen overdose. NAC, a glutathione donor, is the antidote for acute acetaminophen toxicity, and it has been shown to improve outcome in these patients. Importantly, it is most effective if administered within 8-24 hours of the overdose (24), which significantly limits its therapeutic impact. It is mainly of benefit in patients who take an intentional overdose and then present rapidly for medical care. Cases of accidental overdoses often present for medical attention after the effective window for NAC has closed. Similarly, patients taking an intentional overdose who do not seek care often present too late for NAC to be of maximum benefit (25). Recently, a controlled blinded study of NAC has shown evidence that it benefits non-acetaminophen-related ALF if given during early stages of encephalopathy (26).

Thus, for the vast majority of patients with ALF, liver transplantation is the only recognized treatment option. However, some patients cannot be transplanted due to the severity of their disease or a concomitant medical condition, and even patients who are listed may die waiting for a suitable organ to come available. Transplantation is far from an ideal treatment, as short-term survival for patients with ALF is lower than for cirrhosis, with a 90% 1-month survival and 70% one-year survival (27, 28). Transplantation also commits the patient to a lifetime of immune-compromising and toxic anti-rejection medications. Additionally, some neurocognitive sequelae of increased intracranial pressure persist after liver transplantation for ALF.

In summary, therapeutic options in ALF are limited other than supportive care and liver transplantation. NAC is appropriate for early presentations of acetaminophen overdose and possibly is of value in other forms of ALF. Management of fluid status, airway protection and infection control are important, and, for cerebral edema, mannitol or hypertonic saline are used to osmotically draw water from astrocytes, but are temporizing measures (28). Usually, patients with intracranial hypertension who initially respond to mannitol or hypertonic saline die of cerebral herniation if not transplanted in short order.

The above observations provide a strong rationale for using ammonia-lowering therapy in patients with ALF. Lactulose is widely used for this purpose in patients with cirrhosis, but has not been studied systematically in patients with ALF, and may obscure the surgical field at the time of liver transplantation due to gaseous distention of the bowel (28). Poorly absorbable antibiotics such as neomycin or rifaximin have also not been studied, and the former carries considerable risk of nephrotoxicity. A recent randomized, controlled study of L-ornithine L-aspartate (LOLA), a putative ammonia-lowering agent, found no improvement in blood ammonia concentrations or survival in patients with ALF (29). However, the rationale underlying the use of this agent may be flawed, since the compound provides a substrate (ornithine) for the production of glutamate and theoretically may lower ammonia by production of glutamine, but does not provide a route of glutamine elimination from the body. Thus, glutamine persists in the circulation in patients receiving LOLA, and subsequently may be deamidated back to ammonia and glutamate by gut glutaminases (30).

OCR-002 (ornithine-phenylacetate; OPA) is an ammonia detoxification agent with a better rationale for use in patients with hyperammonemia than LOLA. In contrast to LOLA, OPA not only provides a substrate for the synthesis of glutamate and thus glutamine, but also a route of elimination of glutamine in the urine as phenylacetylglutamine (PAGN) (14). The synergistic effects of L-ornithine and phenylacetate have been documented in validated pharmacology models of liver failure, the devascularized ALF pig and the bile-duct ligated cirrhotic rat (31, 32). In these animal models, reduction of the central target of OPA, ammonia, correlated with improvement in intracranial pressure and frontal brain water, which are associated with HE, as well as morbidity and mortality in humans with ALF. The mechanism supporting elimination of glutamine *via* PAGN in urine has been confirmed in both models and supports the utility of the combination therapy for removal of waste nitrogen (ammonia) from the body. Another important feature of OPA pertains to the ability of PAGN to be dialyzed (33), a critical observation as many patients with ALF develop acute renal failure requiring renal replacement therapy.

Patients with acetaminophen toxicity leading to acute liver injury or liver failure are optimal patients for the planned clinical study for several reasons. First, their liver injury is severe and occurs very rapidly over a prescribed time course, considered hyperacute (< 7 days) in duration. Second, acetaminophen patients comprise a large, relatively homogeneous patient group, are typically young and otherwise healthy. Third and most importantly, they are at the highest risk for elevated ammonia levels and cerebral edema because of their young age and the rapidity of their liver failure. Renal failure can also be observed in this setting, presumed due to a direct effect of the drug on the renal tubular cells, and contributes to hyperammonemia and the risk of cerebral edema. Although the overall recovery rate is quite high after acetaminophen overdose despite the severity of the liver injury, many patients cannot be listed for transplantation because of the psychosocial issues which contributed to the overdose.

In the current protocol, all patients will have been treated with NAC as standard-of-care for acetaminophen toxicity. There are no anticipated interactions between NAC and OCR-002 based on the pharmacology of each compound. All patients who are enrolled will have received appropriate management for acetaminophen toxicity, including N-acetylcysteine either oral or intravenous, prior to study enrollment. In some instances, this will be continued

during, or may overlap with, the study period.

This Phase 2a clinical study is designed to provide data on OCR-002 in patients with ALF/ALI in regard to:

- (a) safety and tolerability;
- (b) metabolism of the compound to glutamine and phenylacetylglutamine;
- (c) its effect on circulating ammonia levels and neurological function in patients with and without impaired renal function after continuous infusion at different infusion rates.

It is anticipated that this early safety and tolerability study, with appropriate PK/PD data, will lead to a development program for the use of OCR-002 in the treatment of hyperammonemia either due to ALF or even more generally, for ACLD.

3.3.2 Rationale for Dose Selection

Ocera Therapeutics, Inc. (Durham, NC) has conducted two clinical trials evaluating safety, tolerability and pharmacokinetics in healthy volunteers (n=48) and stable cirrhotic patients (n=43).

Clinical study OCR-002 HE201 was designed as a randomized, placebo-controlled, dose-ranging study, evaluating doses (i.v. infusion) of 1, 3, 10, 20 and 30g given over 4h, and 30, 40 and 60g given over 24h. Following a single ascending dose phase, a multiple ascending dose phase (5d of consecutive administration) for doses of 1, 3, 10 and 20g given over 4h was assessed. The key findings in this study included:

There were no deaths, SAE or AE discontinuations in the study.

A dose related increase in the incidence and severity of adverse events was observed.

Commonly occurring adverse events that appeared to be related to dose included dizziness, somnolence, headache, nausea/vomiting and tinnitus.

There was no evidence to suggest that AEs increased or new AEs occur with multiple dosing.

With respect to blood pressure, there were no apparent trends from placebo with respect to mean changes from baseline; however at dose levels $\geq 20\text{g}/4\text{h}$, several patients experienced clinically significant orthostatic hypotension.

There appeared to be a dose and exposure related increase in mean heart rate starting at a dose level of $10\text{g}/4\text{h}$ and higher. These effects also persisted for longer periods in the higher dose groups.

20g administered over 4 h was the maximum tolerated dose (MTD), however, doses of $10\text{g}/4\text{h}$ and below were well tolerated.

24h Holter monitor recording identified a dose-related increase in heart rate accompanied by modest effects on ventricular repolarization as measured by QT. These effects should be interpreted with caution in light of the small sample size and higher heart rates observed in this study.

There were no clinically significant abnormal laboratory parameters and no patient had any clinically significant changes in physical examination findings or mean

change in body weight between baseline and follow up.

Doses higher than 10g/4h are associated with adverse effects that may be rate and C_{max} related and are likely associated with the non-linear pharmacokinetic profile of phenylacetate above 10 g.

A slower infusion rate (24hr-infusion) avoids C_{max} related adverse effects while providing similar excretion of PAGN.

In aggregate, these studies supported an initial study using a 10g/24 hours dose of OCR-002 as suitable for an early phase study in ALF patients. As STOP-ALF represents the first study of OCR-002 conducted in patients with ALF, the administration of the study drug in three ascending dose levels (Dose Levels 1 through 3) will be implemented as follows and in the protocol for up to 24 evaluable subjects:

The maximum target infusion rate will be 0.42g/h, which is equivalent to 10g administered over 24h.

The infusion rate will be staged for each patient. The initial infusion rate will be 0.14g/h (33% of target dose). The dose will be then increased to 0.28g/h (66% target), and 0.42g/h (100% target) in successive 12h intervals based on a patient safety evaluation by the Investigator.

Patient safety and tolerability at an increased loading dose are supported by the pharmacokinetic data and plasma ammonia levels obtained from the ongoing clinical study Phase 2 OP-GIB conducted in Spain, in which cirrhotic patients with active gastrointestinal hemorrhage receive double-blind treatment, i.e., placebo or OCR-002 at 10 g per 24 hours as a constant intravenous infusion for 5 days.

Ocera began over a year ago a large ongoing trial of OCR-002 in hospitalized patients with cirrhosis and associated hyperammonemia (OCR002-HE209, STOP-HE). In STOP-HE, a placebo-controlled, randomized, double-blind clinical trial designed to evaluate the safety, pharmacokinetics and efficacy of intravenously-administered OCR-002 in resolving neurocognitive symptoms of acute HE in hospitalized cirrhotic patients with elevated ammonia, either OCR-002 or placebo is administered to patients intravenously for up to five days along with standard of care, at doses of 20, 15, or 10 grams over 24 hours based on the patient's degree of liver impairment. In this study, there is no ascending or loading dose being implemented.

Therefore, up to 12 additional evaluable patients will be enrolled at Dose Level 4 as listed below:

Dose Level 4: For patients assigned to this dose level, the infusion will be initiated at the full dose level of 20g/24hr for a maximum time of 120 hours (approximately .83g/h), provided the dose level is well tolerated with no noteworthy side effects.

4 OBJECTIVES AND ENDPOINTS

4.1 *Objectives*

4.1.1 **Primary Objective**

To evaluate the safety and tolerability of OCR-002 in patients with acute liver failure/severe acute liver injury.

Hypothesis: Treatment with OCR-002 is safe and tolerable in patients with acute liver failure/acute liver injury.

4.1.2 **Secondary Objectives**

To evaluate the steady state pharmacokinetic and pharmacodynamic profile of OCR-002 in patients with impaired and minimal renal dysfunction using urinary PAGN as a surrogate marker.

Hypothesis: A dose of 10-20g/24h (0.42-.83g/h) will achieve steady state plasma concentrations within 6-12h with little additional accumulation in the ALI/ALF setting.

To evaluate the effect of OCR-002 on ammonia levels in patients with acute liver failure/severe acute liver injury.

Hypothesis: Treatment with OCR-002 will reduce ammonia levels in patients with ALI/ALF.

To evaluate the effect of OCR-002 on neurological function in patients with acute liver failure/severe acute liver injury.

Hypothesis: Treatment with OCR-002 will improve neurological function in patients with acute liver failure/severe acute liver injury.

4.2 *Endpoints*

4.2.1 **Safety Endpoints**

Safety assessments will include: abbreviated physical examinations, vital signs (blood pressure, pulse rate, respiration rate, and body temperature), clinical laboratory tests (hematology and serum chemistry), 12-lead ECGs, and reported and observed adverse events.

4.2.2 **Exploratory Efficacy Endpoints**

- Ammonia concentrations.
- Neurological assessment will be measured by the Glasgow Coma Scale, the West Haven Criteria, and the Orientation log (O-log) (34).

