2 PROTOCOL SYNOPSIS

Protocol Number/Title	ALFSG-OCR-002: A Phase 2a Study to Evaluate the Safety and Tolerability of OCR-002 (ornithine phenylacetate) in the Treatment of Patients with Acute Liver Failure/Severe Acute Liver Injury (STOP-ALF)
Phase	Phase 2a
Objectives	
Primary Objectives:
 
To evaluate the safety and tolerability of OCR-002 in patients with acute liver failure/severe acute liver injury
 
Secondary Objectives:
 
To evaluate the steady state pharmacokinetic and pharmacodynamic profile of OCR-002 in patients with minimal renal dysfunction using urinary PAGN as a surrogate marker
 
To evaluate the effect of OCR-002 on ammonia levels in patients with acute liver failure/severe acute liver injury
 
To evaluate the effect of OCR-002 on neurological function in patients with acute liver failure/severe acute liver injury

Study Chair	[name], UT Southwestern Medical Center, Dallas, TX
Co-Principal Investigators	[name], University of Michigan, Ann Arbor, MI R. [name], VCU Medical Center, Richmond, VA
Investigative Sites	Approximately 6-12 investigative sites in the United States

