Study Design	
This is a Phase 2a, multi-center, open-label study, conducted in two cohorts of patients diagnosed with acute liver failure/severe acute liver injury (ALF/ALI) who meet inclusion/exclusion criteria. Cohort 1 is defined as patients with ALF/ALI with minimal renal dysfunction at the time of enrollment (defined as a serum creatinine ≤ 1.5 mg/dL and mean arterial pressure of >65 mm Hg). Cohort 2 is defined as patients with ALF/ALI with compromised renal function (defined as a serum creatinine >1.5 mg/dL and <10 mg/dL with mean arterial pressure of >65 mm Hg).
 
Informed consent will be obtained from the patient and/or patient's legally authorized representative (LAR) or family member as defined in 21CFR50.3(m). All patients will receive medical care for acute liver failure/severe acute liver injury according to the institution's standards of care. Standard of care may include, but is not limited to, administration of N-acetylcysteine and consideration for orthotopic liver transplantation.
 
Up to 36 evaluable patients will be enrolled. An evaluable patient is one who has received an infusion of OCR-002 for at least 72 hours. It is expected that not every enrolled patient will be treated for at least 72 hours due to transplant, death or early hospital discharge. Due to this, we anticipate 25% of the enrolled population will fail to reach evaluable status. Therefore, we plan to enroll up to 50 patients in order

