Treatment Continued	
experiences CTCAE grade 1 or 2 adverse reactions or intolerance to the assigned dose, the investigator may choose to titrate back to the lower tolerated dose and closely monitor the patient. The infusion rate and dose may be discontinued if the patient experiences CTCAE grade 3 or higher, or any time at the investigator's discretion. Each dose level between 1 and 3 will be administered to Cohort 1 patients and safety and PK data reviewed, prior to exposing Cohort 2 patients to the study drug and subsequent dosing levels. Dose level 4 will be administered to both Cohort 1 and 2 beginning simultaneously.
 
The dosing levels for Dose Levels 1 through 3 are defined follows:
 
Dose Level 1:
 
Patients will receive the initial infusion of study drug at 0.139 g/h for the first 12 hours (approximately 3.33 g/24h or 6.9 mL/h) and be maintained at this rate for up to 5 days.
 
Dose Level 2:
 
For patients assigned to this dose level, the infusion will be initiated at 0.139 g/h for the first 12 hours (approximately 3.33 g/24h) and increased to 0.277 g/h (approximately 6.65 g/24h or 13.8 mL/h) for the remainder of the treatment period.
 
Dose Level 3:
 
For patients assigned to this dose level, the infusion will be initiated at 0.139 g/h for the first 12 hours (approximately 3.33 g/24h), increased to 0.277 g/h (approximately 6.65 g/24h) for the next 12 hours, and then increased to 0.416 g/h (approximately 10 g/24h or 20.8 mL/h) for the remainder of the treatment period.
 
The dosing level for Dose Level 4 is defined follows:
 
Dose Level 4:
 
For patients in Cohorts 1 and 2, the infusion of OCR-002 will be initiated at 20g/24hr for a maximum time of 120 hours (approximately .83g/h), provided the dose level is well tolerated with no noteworthy side effects.
 
Initiation of each higher dose for patients in Dose Levels 1 through 3 and continuation of study drug administration for patients in Dose Level 4 will occur only if there are no treatment emergent SAEs of CTCAE Grade 4 or higher that are not attributed to acute liver failure in the opinion of the investigator.
 
In all dose levels, if 1 out of the 3 patients within a dose group experiences a treatment emergent SAE of CTCAE Grade 3 that is not attributed to acute liver failure, then an additional patient will be enrolled into that specific dose group. Within a given dose level, if 2 or more patients experience a treatment emergent SAE of CTCAE Grade 3 that is not attributed to acute liver failure in the opinion of the investigator, then dose escalation (Dose Levels 1 through 3) or continuation of study drug administration (Dose Level 4) will stop. Dose escalation or continuous administration also will stop if 1 patient experiences a Grade 4 or higher SAE that is not attributed to acute liver failure in the opinion of the investigator. Otherwise, dose escalation and continuous study drug administration will continue to the maximum tolerated dose and the remaining enrolled patients will be treated at this dose. Further details of dose

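### The synopsis and Section 4.1.2 name different populations for the urinary PAGN objective, and the planned urinary PAGN summary separates neither renal replacement therapy nor dose level

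*Combined protocol and SAP*

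**What the plan says.** The two statements of the same secondary objective differ. In the synopsis (Objectives) it applies "in patients with minimal renal dysfunction using urinary PAGN as a surrogate marker". In Section 4.1.2 it applies "in patients with impaired and minimal renal dysfunction using urinary PAGN as a surrogate marker".

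Section 3.3.1 gives the background on dialysis: "Another important feature of OPA pertains to the ability of PAGN to be dialyzed", which it treats as critical because "many patients with ALF develop acute renal failure requiring renal replacement therapy". Section 5.1 has continuous hemodialysis considered for Cohort 2 patients with creatinine of 2.0 or more. The Supportive Care text (synopsis and Section 5.1) allows dialysis or hemofiltration as indicated, without restricting it to one cohort. Cohort is fixed by creatinine at enrolment, and Section 6.1 keeps each patient in a single cohort.

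For PAGN output, Sections 5.1 and 8.3 describe timed urine collection only, with no dialysate or effluent. Section 5.1 intends the urine result to inform synthesis of PAGN as well as excretion.

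Section 11.7.6 plans individual listings and a mean of cumulative urinary PAGN. Sections 11.2 and 11.6 group results overall and by cohort. Neither RRT nor dose level is a grouping. The closing memorandum confirms that there is no separate SAP.

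**The concern.** Urinary PAGN is the named surrogate for this objective and one source of evidence for aim (b) in Section 3.3.1, "metabolism of the compound to glutamine and phenylacetylglutamine". PAGN excretion also mattered in choosing the regimen: Section 3.3.2 credits the slower infusion with avoiding C_max "related adverse effects while providing similar excretion of PAGN".

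A low cohort mean could arise from PAGN lost into dialysate, from retention in renal impairment, from a low assigned dose, or from poor conversion of the drug. Only the last bears on whether the mechanism works in these patients. The planned means do not separate the four. Because the objectives disagree, it is also unclear whether the surrogate is meant to be read in Cohort 2 at all, which is where RRT is most likely to be considered.

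**Working it through.** **1. Population.** The synopsis names minimal renal dysfunction (Cohort 1). Section 4.1.2 adds impaired patients (Cohort 2). Neither text is marked as superseded. Urine collection in all patients and reporting by cohort fit Section 4.1.2 better. Choosing the synopsis wording would not remove the RRT question, because a Cohort 1 patient may start RRT after enrolment.

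**2. Direction of the RRT effect.** Let U be PAGN recovered in urine and D be PAGN removed by RRT during collection. Elimination by the two routes is U + D, and the plan measures U. The understated share is D/(U + D), which is above zero whenever D > 0. The protocol's statement that PAGN can be dialyzed implies D > 0 on RRT.

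**3. Size of the RRT effect.** The documents give neither D/U nor the share of patients on RRT. Purely as an assumption, D/U from 0.25 to 4 gives 0.25/1.25 = 20% up to 4/5 = 80%. A range that wide shows only that the assumption decides the answer, so no size is claimed.

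**4. Scheduled dose.** Rates come from the synopsis (Treatment) and Section 5.2. They reproduce the plan's own daily figures: 0.139 × 24 = 3.34 g, 0.277 × 24 = 6.65 g and 0.416 × 24 = 9.98 g; 20/24 = 0.83 g/h.

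The time limits are the evaluability rule, "An evaluable patient is one who has received an infusion of OCR-002 for at least 72 hours", and the maximum, which for Dose Level 4 reads "the infusion of OCR-002 will be initiated at 20g/24hr for a maximum time of 120 hours". Total dose is the sum of rate × hours:

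| Dose Level | 72 h | 120 h |
|---|---|---|
| 1 | 0.139×72 = 10.0 g | 0.139×120 = 16.7 g |
| 2 | 0.139×12 + 0.277×60 = 18.3 g | 0.139×12 + 0.277×108 = 31.6 g |
| 3 | 0.139×12 + 0.277×12 + 0.416×48 = 25.0 g | 0.139×12 + 0.277×12 + 0.416×96 = 44.9 g |
| 4 | (20/24)×72 = 60 g | (20/24)×120 = 100 g |

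The ratio of Level 4 to Level 1 is 60/10.0 = 6.0 at 72 h and 100/16.7 = 6.0 at 120 h. These are scheduled doses, before any down-titration.

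**5. What a cohort mean would pool.** Section 3.3.2 allows up to 24 evaluable patients at Dose Levels 1 to 3 and up to 12 at Dose Level 4. Section 5.1 plans three per cohort at Levels 1 and 2, which leaves 24 − 12 = 12 for Level 3. Assume an equal split by cohort (3, 3, 6, 6) and 120 h for everyone. The mean dose is then (3×16.7 + 3×31.6 + 6×44.9 + 6×100)/18 = 56.4 g, which matches no dose level.

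**The case against.** **The effect is limited.** The study is descriptive, with no sample-size calculation, and Section 4.2 lists no urinary PAGN endpoint. The hypothesis under this objective concerns plasma steady state. Individual urinary values and plasma PAGN are both listed, and the Safety Review Committee sees data by dose level during the trial, so a careful reader could link values to dose. This largely stands and keeps the point small. It does not cover RRT: Section 8.3 lists no RRT times, so unless the CRF (not supplied) captures them, the link may not be recoverable. In-trial reports to the committee are also not the final analysis in Section 11.

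**Dose pooling is not special to urinary PAGN.** True: it follows from Sections 11.2 and 11.6. It is raised here because cumulative output depends directly on how much drug was given, and because an RRT split that ignored dose could mislead.

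**Stronger readings that the documents do not support:**
- *The Cohort 2 mean certainly mixes patients on and off RRT.* Section 5.1 says only that RRT will be considered, so the mix is possible in either cohort and certain in neither.
- *The dose spread is wider than 6-fold.* Comparing Level 1 at 72 h with Level 4 at 120 h gives a larger ratio, but it mixes dose level with duration.
- *PAGN output also differs 6-fold.* The figure is for dose. Section 3.3.2 reports non-linear phenylacetate kinetics at higher doses in the earlier study, so proportional output cannot be assumed.
- *RRT also distorts ornithine and phenylacetate clearance.* The documents call only PAGN dialyzable.

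**Conclusion.** The point holds within limits. The two statements of the objective conflict and must be reconciled. In any patient who receives RRT during collection, urinary PAGN understates PAGN elimination. This rests on the protocol's statement that PAGN is dialyzable and on urine being the only matrix described; its size is unknown. Followed as written, Section 11 gives means that count dialysate loss as low excretion or synthesis and pool dose levels with a 6-fold spread in scheduled dose at equal duration.

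The consequence is confined to interpreting the urinary surrogate. The plasma steady-state hypothesis and the ammonia, neurological and safety aims are not affected, and aim (b) is also informed by plasma PAGN. The documents do not say whether urinary PAGN is among the PK data that the Safety Review Committee reviews. Importance is minor to moderate: worth correcting because correction is cheap.

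**What to change.** 1. State one population for the urinary PAGN objective in the synopsis and Section 4.1.2.
2. In Section 11.7.6, summarise cumulative urinary PAGN by dose level within cohort, with infusion duration shown.
3. Record RRT start and stop times if the CRF does not already do so. Flag RRT status and dose level in the individual urinary and plasma PAGN listings. Show the urinary summary with and without patients who had any RRT during collection, giving n and making no formal contrast.
4. State that PAGN removed by RRT is not measured, so that urinary PAGN is not read as total elimination or synthesis in those patients.

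Scaling each interval's output per gram infused is not recommended. Output may lag the infusion, RRT may affect later intervals, plasma samples fall on interval boundaries, and proportionality to dose is not established.

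**Cost:** wording in the synopsis or Section 4.1.2 and in Section 11.7.6, some table work, at most one CRF item, and no new samples.

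**Downsides:** cells are very small, with three patients planned per cohort at each of Dose Levels 1 and 2. The RRT-free subset will be smaller and probably less ill, and any RRT removes that patient's whole cumulative value from it. Grouping by assigned level does not correct for down-titration. None of this recovers PAGN lost in dialysate.
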